10.1 Randomization for Phase II Study

Steroids is the most commonly used SOC therapy for irAEs. It affects the severity and duration of irAE, which are the key endpoints of this study. We thus will stratify the subjects based on the status of steroids use at registration. Stratified block randomization will be used. Randomization codes will be generated in a permuted block design, stratified by the status of steroids use at registration. The block size will be balanced within each block to maintain a 1:1 ratio between the two groups. For patient who have no steroids use at registration but start on steroids before starting CD24Fc treatment, the patient will be moved to the steroid stratum. If a subject withdraws from participation in the study or changed to steroids use group, his or her randomization code will not be re-used.

10.2 Statistical Analysis

Demographic and background characteristics obtained at enrollment will be listed and summarized. Descriptive statistics will be used to summarize changes of biomarkers from baseline in clinical laboratory parameters for this cohort, and use of steroids (drug, dose, duration) and other treatment for irAE. We will adjust steroids use in analyses. Subgroup analyses will be performed separately by the status of Steroids use.

To assess toxicity: Toxicity is evaluated by NCI CTCAEv5.0. The type, grade, frequency and proportion of toxicities noted during the treatment period will be reported, along with associated 95% confidence interval of proportion. All adverse events noted by the investigator will be tabulated according to the affected body system. In phase I lead-in study, dose limiting toxicity is defined as any new AE of \geq grade 3 that are outside the spectrum of irAEs.

To assess time to recovery from irAE (time to reduction of irAE by at least one grade), time to all irAEs reduced to ≤ 1 , and time to resume ICI treatment: All time points will be started from Day 1 of CD24Fc treatment. Kaplan-Meier plots and confidence intervals will be used to summarize outcomes. Medians and associated 95% confidence intervals will be calculated, and comparisons between groups will be

performed by log-rank tests. Cox proportional hazard models will be used to explore association between covariates and outcomes.

To assess recovery rate of CD24Fc (reduction of irAE by at least one grade) at D42 and response rate of ICI: The fraction of patients who experience a PR or CR will be determined by dividing the number of responders by the total evaluable patients. The fraction will be reported along with 95% two-sided confidence intervals. Comparisons between groups will be performed by Fisher's Exact tests. We will also characterize the proportion who remain that either respond or have stable disease, compared to those who progress.

To assess PFS and OS: Kaplan-Meier plots and confidence intervals will be used to summarize PFS, and OS; 1-year OS rate will be reported; medians and associated 95% confidence intervals will be calculated, and comparisons between groups will be performed by log-rank tests. Cox PH models will be used to explore association between outcomes and covariates.

As exploratory analysis, we will summarize descriptively the relationship of response rates to tumor type (lung, breast, prostate) and to cellular immune response, and explore the relationship using logistic regression.

The possibility of bias from missing data will be addressed. Missing pattern and mechanism will be evaluated, and sensitivity analyses will be performed using imputation methods for use of steroid, irAE type, cancer type, etc., if such might affect point estimates and study conclusions.

The study design in the Phase II portion allows steroids and other systemic treatments prior to and during study enrollment. CD24Fc/placebo will be added in addition to standard of care. We will perform a sensitivity test for data from the Phase II study. We will consider isolating the effect of CD24Fc in the future Phase III clinical study.

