	
Demographic and background characteristics obtained at enrollment will be listed and summarized. Descriptive statistics will be used to summarize changes of biomarkers from baseline in clinical laboratory parameters for this cohort, and use of steroids (drug, dose, duration) and other treatment for irAE.
 
To assess toxicity: Toxicity is evaluated by NCI CTCAEv5.0. The type, grade, frequency and proportion of toxicities noted during the treatment period will be reported, along with associated 95% confidence interval of proportion. All adverse events noted by the investigator will be tabulated according to the affected body system. In phase I lead-in study, dose limiting toxicity is defined as any new AE of \geqgrade 3 that are outside the spectrum of irAEs.
 
To assess time to recovery from irAE (time to reduction of irAE by at least one grade), time to all irAEs reduced to \leq1, and time to resume ICI treatment: The date of starting treatment (i.e., Day 1) will be used for all time events in the study. Kaplan-Meier plots and confidence intervals will be used to summarize outcomes. Medians and associated 95% confidence intervals will be calculated, and comparisons between groups will be performed by log-rank tests. Cox proportional hazard models will be used to explore association between covariates and outcomes.
 
To assess recovery rate of irAE by CD24Fc (reduction of irAE by one grade) at D42 and response rate of ICI: The fractions will be reported along with 95% two-sided confidence intervals. Comparisons between arms will be performed by Fisher's Exact tests. We will also characterize the proportion who remain that either respond or have stable disease, compared to those who progress.
 
To assess PFS and OS: Kaplan-Meier plots and confidence intervals will be used to summarize PFS, and OS; 1-year OS rate will be reported; medians and associated 95% confidence intervals will be calculated, and comparisons between groups will be performed by log-rank tests. Cox PH models will be used to explore association between outcomes and covariates.
 
As exploratory analysis, we will summarize descriptively the relationship of response rates to tumor type (lung, GI, melanoma, breast, prostate) and to cellular immune response and explore the relationship using logistic regression.

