	
The possibility of bias from missing data will be addressed. Missing pattern and mechanism will be evaluated, and sensitivity analyses will be performed using imputation methods for use of steroid, irAE type, cancer type, etc., if such might affect point estimates and study conclusions.
 
Sample Size Justification
 
Phase I study:
 
We plan to enroll 6 patients in the phase I study. The objective of this phase I study is to confirm the safety of CD24Fc in ICI-treated cancer patients who have treatment interruption due to grade 2 or 3 irAEs and to estimate the median time to recovery and resumption of ICI after treatment interruption due to irAE. The primary endpoint is new AE of \geqgrade 3 that are outside the spectrum of irAEs when CD24Fc is given to treat irAEs. We expect the rate of this event will be less than 33.3%. With a sample size of 6 patients, we would have 74-91% chance to observe at least one occurrence if the true event rate is 20-30%. Hence the sample size is adequate for this pilot study for safety.
 
Randomized phase II study:
 
Previous studies suggested that response rate at 42 days for control group will be about 50%. We hypothesize CD24Fc will increase recovery rate from 50% to 80 %. A sample size of 72 patients (36 in each arm) will have 81% power to detect an increase of recovery rate from 50% of control group to 80% of CD24Fc group. This result is based on one-sided Fisher's Exact test and significance level of 0.05. Group-sequential design will be used with interim analysis to monitor the trial by a cohort size of 24 (12 in each group), with maximum sample size of 72, average sample size of 46 if null hypothesis is true, and 58 if alternative hypothesis is true.
 
Steroids is the most commonly used SOC therapy for irAEs. It affects the severity and duration of irAE, which are the key endpoints of this study. We thus will stratify the subjects based on the status of steroids use at registration and will adjust steroids use in analyses. Few patients might start on steroids as SOC before starting the study treatment, and the patients will be moved to the steroid stratum.

Estimated Accrual/Enrollment Period:	Six patients in the phase I study and 72 patients in phase II randomized study. Of about 50 cancer patients received ICI per month at UCD, 8 patients (15%) develops grade 2 and 3 irAE that require treatment interruption. We estimate 4-5 patients will be enrolled each month.

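### Phase II randomisation is stratified by steroid use and adjustment is promised, but the tests named for both co-primary endpoints use no strata, and the steroid status for adjustment is undefined

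*Combined protocol and SAP*

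**What the plan says.** Section 10.1 randomises Phase II in permuted blocks, 1:1, stratified by steroid use at registration. The reason given is that steroids influence how severe the irAE is and how long it lasts. The Synopsis (Sample Size Justification) says subjects are stratified on the "status of steroids use at registration and will adjust steroids use in analyses", and section 10.2 repeats "We will adjust steroids use in analyses".

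The between-arm tests for the co-primary endpoints are these:

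- **Day 42 recovery:** "Comparisons between groups will be performed by Fisher's Exact tests" (10.2); the Synopsis has "Comparisons between arms will be performed by Fisher's Exact tests".
- **Time to recovery:** "comparisons between groups will be performed by log-rank tests" (Synopsis and 10.2), with no mention of strata.

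Steroid status could also enter in two other places in 10.2. One is exploratory: "Cox proportional hazard models will be used to explore association between covariates and outcomes". The other is by subgroup: "Subgroup analyses will be performed separately by the status of Steroids use". The logistic regression in 10.2 concerns tumour response, and the sensitivity test mentioned at the end of 10.2 is not defined.

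On changes of status, the Synopsis notes "Few patients might start on steroids as SOC before starting the study treatment". Section 10.1 transfers such a patient to the steroid stratum and retires the randomisation code. It does not say whether the patient stays in the arm already assigned or receives a new code.

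**The concern.** A Fisher's exact test on a single 2×2 table cannot adjust for anything, so the promised adjustment has no place in the named analysis of the first co-primary endpoint. For the second, a log-rank test can be stratified, but the plan does not say that it is.

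Three things are at stake.

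- **Efficiency.** When randomisation is balanced within a prognostic stratum and the test ignores that stratum, the test is conservative: its true size falls below nominal and some power is lost.
- **Choice of steroid variable.** Status at registration, status after the pre-dose transfer and use during treatment all fit the promise. The third would condition on something measured after randomisation. It is also a Phase II secondary endpoint, and section 1.1 expects CD24Fc to reduce steroid treatment.
- **Arm of transferred patients.** Without a rule, the arm in which such a patient is treated and analysed is open.

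As written, the adjustment method and the analysis stratum could be chosen after the results are known.

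**Working it through.** **Inputs from the plan (10.3):** 36 patients per arm, recovery 50% vs 80% at Day 42, one-sided Fisher's exact test at 0.05, stated power 81%.

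**Assumed inputs.** The plan gives neither the steroid share nor recovery by stratum, so these are varied, holding 50% and 80% overall. The treatment effect is common to both strata. The plan gives no sidedness for the log-rank test; one-sided 0.05 is assumed.

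**Step 1, the plan's own figure.** With t CD24Fc and c control recoveries, the Fisher p-value is P(H ≥ t), H ~ Hypergeometric(72 patients, c+t recoveries, 36 drawn). Summing the probability of p ≤ 0.05 over two Binomial(36) arms gives power 80.9% and size 3.8% at 50% vs 50%. The stated 81% is reproduced. It belongs to the unstratified test at a single look.

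**Step 2, Day 42 recovery.** For stratum j with n_j per arm and m_j recoveries in all, the exact stratified p-value is P(H₁+H₂ ≥ t), H_j ~ Hypergeometric(2n_j, m_j, n_j). The CD24Fc rate in each stratum is ψp_j/(1−p_j+ψp_j), with the odds ratio ψ solved so that the overall CD24Fc rate is 80%. For 75%/25%, ψ = 5.70 gives 4.275/4.525 = 94.5% and 1.425/2.175 = 65.5%, mean 80%. Full enumeration gives:

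| Strata per arm | Control recovery | ψ | Fisher power | Exact stratified power | Fisher size |
|---|---|---|---|---|---|
| 18+18 | 50%/50% | 4.00 | 80.9% | 80.9% | 3.8% |
| 18+18 | 60%/40% | 4.20 | 81.2% | 81.5% | 3.5% |
| 18+18 | 65%/35% | 4.49 | 81.7% | 82.6% | 3.15% |
| 18+18 | 75%/25% | 5.70 | 83.4% | 87.4% | 2.0% |
| 24+12 | 60%/30% | 4.50 | 81.7% | 82.7% | 3.2% |
| 24+12 | 66.7%/16.7% | 6.13 | 83.6% | 88.3% | 2.2% |

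The exact stratified test has size 2.8–3.6% throughout. An uncorrected Cochran-Mantel-Haenszel (CMH) test has higher power (86.8% with no stratum effect), but that gain comes from being less discrete than Fisher, not from stratifying. Its size reaches 5.3–5.4% in some scenarios.

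**Step 3, time to recovery.** Recovery is exponential, read at the visits on Days 14, 28, 42 and 60. The hazard ratio h solves the average of 1−(1−p_j)^h = 80%. With no stratum effect, h = ln 0.2/ln 0.5 = 2.32. There were 40,000 simulated trials per scenario (standard error about 0.1 points):

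| Strata per arm | Control recovery | Log-rank power | Stratified log-rank power |
|---|---|---|---|
| 18+18 | 50%/50% | 92.8% | 92.6% |
| 18+18 | 65%/35% | 93.5% | 95.8% |
| 18+18 | 75%/25% | 95.4% | 99.2% |
| 24+12 | 60%/30% | 93.4% | 95.8% |
| 24+12 | 66.7%/16.7% | 95.3% | 99.4% |

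For the three equal-strata rows, the size is 5.2%, 4.1% and 2.5% without strata and 5.2%, 5.2% and 5.3% with them.

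**Step 4, interim looks.** The Synopsis describes looks every 24 patients but gives no boundary. Three-look efficacy boundaries were therefore assumed, with 6+6 per arm added at each look (400,000 trials). Fisher vs exact stratified power at 50%/50%, 65%/35% and 75%/25% is:

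- O'Brien-Fleming type (nominal p 0.0016, 0.0182, 0.0439): 79.3% vs 79.5%, 80.1% vs 82.1%, 81.7% vs 86.4%.
- Pocock type (nominal p 0.0231 at each look): 71.5% vs 72.1%, 71.8% vs 75.4%, 72.1% vs 80.4%.

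The stratified size is at most 3.0%. No futility rule was modelled.

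**The case against.** The strongest reply is that little is lost. At 55%/45%, Fisher and the exact stratified test both have 81.0% power; at 60%/40% the gain is about 0.3 points. Gains of 4 to 5 points at Day 42 need control recovery to differ by 50 points between strata, and odds ratios of 5.7 to 6.1 against 4.0 for the plan's overall rates. The named tests deliver about 81% or more in every single-look scenario. Section 10.1 speaks of balance between arms, which the design achieves whichever test is used. All of this stands, and it limits the size of the benefit.

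It can also be said that the promise to adjust opens 10.2 and so governs what follows, and that the log-rank test is nowhere called unstratified. That shows intention. It does not supply a method, and no reading lets a plain Fisher test adjust.

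The transfer rule in 10.1 does suggest status at first dose, and under blinding a pre-dose steroid start should not depend on arm, so that definition is defensible too. But the rule sits in the randomisation section, is not tied to the analysis and leaves the patient's arm open.

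Finally, the interim results rest on assumed boundaries. The Synopsis's average sample size of 46 under the null suggests stopping that efficacy boundaries alone would not produce. The interim figures therefore do not verify the actual design.

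**Conclusion.** The concern holds and should be fixed. The plan stratifies on a factor it calls influential and promises to adjust for it, then names a primary test that cannot adjust and another not said to. It leaves undefined both the steroid variable and the arm of transferred patients.

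No stated figure is wrong and type I error is not inflated by ignoring the strata. The power cost depends on assumed stratum effects. At Day 42 it is nil to about 1 point for control differences up to 30 points, and 4 to 5 points for a 50-point difference. For time to recovery it is about 2 points at a 30-point difference and about 4 at 50 points. Confidence is high on the missing specification; the power consequence is conditional on those assumptions. The firmer reason to act is that the adjustment, the stratum and the arm rule should be fixed before unblinding.

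**What to change.** **In 10.2 and the Synopsis:** name as the primary tests an exact stratified test for Day 42 recovery and a stratified log-rank test for time to recovery. Stratify both by steroid status at registration, as used in the original randomisation. CMH is an alternative for Day 42 if a size slightly above 5% is acceptable. Use status after the pre-dose transfer as a sensitivity analysis only, and state that steroid use during treatment is not an adjustment variable for the primary comparison.

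**In 10.1:** state that each patient keeps the originally assigned arm, and that the transfer and the retired code do not lead to a second assignment.

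**In 10.3:** say that the 81% refers to the unstratified single-look test, or restate it for the new primary test.

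**Cost:** the data and sample size are unchanged. If steroids turn out not to be prognostic, nothing material is lost (80.9% vs 80.9%; 92.8% vs 92.6%, within about simulation error). The group-sequential boundaries, including any futility rule, must be re-checked with the stratified test, because the first look would have only about 12 patients per arm divided between strata.

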10.3 Sample Size Justification

Phase I study: We plan to enroll 6 patients in the phase I study. The objective of this phase I study is to confirm the safety of CD24Fc in ICI-treated cancer patients who have treatment interruption due to grade 2 or 3 irAEs and to estimate the median time to recovery and resumption of ICI after treatment interruption due to irAE. The primary endpoint is new AE of \geq grade 3 that are outside the spectrum of irAEs when CD24Fc is given to treat irAEs. We expect the rate of this event will be less than 33.3%. With a sample size of 6 patients, we would have 74-91% chance to observe at least one occurrence if the true event rate is 20-30%. Hence the sample size is adequate for this pilot study for safety.

Randomized phase II study: Previous studies suggested that recovery rate at 42 days for control group will be about 50% [22, 56]. We hypothesize CD24Fc will increase recovery rate from 50% to 80 %. A sample size of 72 patients (36 in each arm) will have 81% power to detect an increase of response rate from 50% of control group to 80% of CD24Fc group. This result is based on one-sided Fisher's Exact test and significance level of 0.05.

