10. STATISTICAL CONSIDERATIONS

10.0 Endpoints

10.0.0 Primary Endpoints

Phase I: Event of new AE of \geq grade 3 that are outside the spectrum of irAEs when CD24Fc is given in cancer patients who developed grade 2-3 irAEs.

Phase II: Co-primary endpoints:

- Recovery rate (as defined by reduction of irAE by one grade) at Day 42.
- Time to recovery from grade 2 or 3 irAE (as defined by reduction of at least 1 grade in irAE severity) from the initiation of CD24Fc treatment. Patients who have not been documented to have event (reduction of at least 1 grade) will be censored at the date of the latest clinical assessment that documented as being free of event.

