10.4 Safety Monitoring and Stopping Rule

The Phase II study is a randomized, double blind, placebo-controlled study. To ensure the safety of the patients enrolled in the Phase II study, Bayesian stopping boundaries are used to allow early stopping at any given time in the combined population. The objective response rate (ORR) and toxicity of CD24Fc during the whole study will be monitored simultaneously using the Bayesian stopping boundaries calculated based on beta-binomial distribution. Toxicity is defined as new AE of \geq grade 3 that are

outside the spectrum of irAEs. ORR is defined as partial response and complete response by RECIST V1.1 after retreatment with ICI.

The regimen will be considered safe if the ORR is at least 20% in all patients in both arms and the toxicity rate is maintained at most 33.3% for the CD24Fc arm. Previous studies for controls suggested the ORR after retreatment with ICI is about 20-40%, and therefore we consider a response rate <20% in all patients in both arms as unacceptable, which will indicate an effect of CD24Fc on promoting tumor growth. The prior probabilities of response and toxicity for the regimen are modeled by beta distributions [Beta(0.8, 1.2) and Beta(0.3, 1.7), respectively], and response and toxicity are assumed to be independent. Denoting the probabilities of response for both arms and toxicity for CD24Fc arm by $\{\theta_{RES}, \theta_{TOX}\}$, and they are compared to fixed targets of response and toxicity rates. The following decision criteria will be applied:

- 1) stop if $\text{Prob}\{\theta_{RES} < 0.2 \mid \text{data}\} > 0.97$, and
- 2) stop if $\text{Prob}\{\theta_{TOX} > 0.333 \mid \text{data}\} > 0.97$

We will have randomization box of 6 patients and thus ensure that 3 patients have been dosed for each 6 subjects enrolled. Patients will be monitored by a cohort size of 6 patients (3 for the CD24Fc arm and 3 for the placebo arm) according to the following stopping boundary for toxicity during the whole study. To be conservative, we attribute all AEs to CD24Fc.

Number of Patients Evaluated in All Enrolled Patients (half control and half CD24Fc)	Stop if Number of ORR Observed	Stop if Number of AE Observed
6	Never stop with these many patients	Never stop with these many patients
12	Never stop with these many patients	≥ 5
18	0	≥ 7
24	≤ 1	≥ 8
30	≤ 2	≥ 10
36	≤ 2	≥ 11
42	≤ 3	≥ 12
48	≤ 4	≥ 14
54	≤ 5	≥ 15
60	≤ 6	≥ 16
66	≤ 7	≥ 17
72	Always stop with this number of patients	

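### Phase I sample size: with six patients, a detection chance of 74-91% does not correspond to event rates of 20-30%; one upper end needs correcting in the synopsis and section 10.3

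*Combined protocol and SAP*

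**What the plan says.** The Phase I justification appears in the same terms in the synopsis (Sample Size Justification) and in section 10.3. The size is fixed first: "We plan to enroll 6 patients in the phase I study". The event counted is a new adverse event of grade 3 or worse that is not one of the immune-related events. An upper limit for its rate follows: "We expect the rate of this event will be less than 33.3" per cent. The operating figure comes next: "we would have 74-91% chance to observe at least one occurrence if the true event rate is 20-30" per cent. The conclusion is drawn directly from it: "Hence the sample size is adequate for this pilot study for safety".

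Section 10.4 uses the same 33.3% again as the Phase II safety limit: the regimen counts as safe on this criterion if the "toxicity rate is maintained at most 33.3% for the CD24Fc arm".

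**The concern.** The statement pairs two ranges, so each end of the probability range should follow from the matching end of the rate range. The number of patients and both rates are given, so nothing has to be assumed from outside to check it. The lower ends agree and the upper ends do not.

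This probability is the only quantitative support for calling six patients adequate for safety. If the 30% is what the authors meant, the plan gives a more favourable chance of seeing a safety signal than six patients provide. If they meant 33.3%, the probability is right and the rate is misprinted. In either case a reader who checks the sentence cannot reproduce it.

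**Working it through.** **Inputs.** n = 6; event rates 20% and 30%; stated probabilities 74% and 91% (synopsis and section 10.3). Limit of 33.3% (the preceding sentence in both places, and section 10.4).

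**Formula.** With independent patients and a common event rate p, the chance of at least one event is 1 - (1 - p)^n.

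**The plan's own figures, n = 6.**

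- p = 0.20: 1 - 0.8^6 = 1 - 0.2621 = 0.7379. This rounds to 74%, as stated.
- p = 0.30: 1 - 0.7^6 = 1 - 0.1176 = 0.8824. This rounds to 88%; the plan says 91%, a gap of 91 - 88.2 = 2.8 points.
- p = 1/3: 1 - (2/3)^6 = 1 - 0.0878 = 0.9122. This rounds to 91%. Using 0.333 gives 0.9119, and 0.33 gives 0.9095; both also round to 91%.

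**Working back from 91%.** The rate that gives exactly 91% with six patients is 1 - 0.09^(1/6) = 0.3306. Allowing for rounding (90.5% to 91.5%), the rate lies between 1 - 0.095^(1/6) = 0.3245 and 1 - 0.085^(1/6) = 0.3369. A 30% rate is outside that interval, so rounding does not explain the difference.

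**Could another input or method explain it?**

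| Variant | At 20% | At 30% |
|---|---|---|
| n = 5, binomial | 67.2% | 83.2% |
| n = 6, binomial | 73.8% | 88.2% |
| n = 7, binomial | 79.0% | 91.8% |
| n = 6, Poisson: 1 - exp(-1.2), 1 - exp(-1.8) | 69.9% | 83.5% |

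None of these gives 74% and 91% together. Only n = 6 with the binomial formula reproduces the 74%, so the number of patients is not the slip.

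**The complement.** The chance of seeing no event in six patients is 11.8% at a 30% rate. The stated 91% implies 9%.

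**The case against.** The strongest reply is that the intended rate is easy to guess. The sentence immediately before names 33.3%, section 10.4 uses the same limit, and at that rate the 91% reproduces. On this reading the 30% is a shortened 33.3%, the probability range is right, and nothing is overstated. This is a fair and plausible account, and it stands as the likelier explanation. It is not settled, because the 20-30% range is printed in both places and nothing in the documents says that the upper end should be 33.3%. It also leaves the sentence wrong as printed.

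A second reply is that no Phase I decision uses this probability. Dose reduction and termination in section 4.1 depend on counts of dose-limiting toxicities, and the report after the sixth patient (section 6.6) rests on the toxicities observed. This stands in full, and it is why the point is minor.

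Two stronger readings are tempting. A reader might infer that the plan definitely exaggerates its ability to detect toxicity; that holds only if 30% is the intended rate. A reader might also infer that six patients are too few; the documents do not support this. They set no minimum detection chance that 88% would fail, and the adequacy claim for a pilot reads the same at 88% as at 91%.

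**Conclusion.** The sentence is wrong as written in both places: with six patients, rates of 20-30% correspond to 74-88%, and 74-91% corresponds to 20-33.3%. The slip is in either the 91% or the 30%. The nearby 33.3% points to the 30%, without proving it.

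The size is 2.8 percentage points at the upper end. If 30% was meant, the chance of missing the event altogether is 11.8% instead of 9%; if 33.3% was meant, no probability changes. The result assumes independent patients with a common event rate and all six evaluable. The mismatch affects neither the sample size, nor the conclusion about adequacy, nor any stopping or dose rule. It is a small correction of fact.

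**What to change.** The authors should decide which rate they meant and make the same edit in the synopsis and in section 10.3. Either keep the rates at 20-30% and change the probability to 74-88%, or keep the probability at 74-91% and change the rates to 20-33.3%.

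The cost is one line in two places, with no added patients and no change to the design. The only disadvantage for the authors is that, if they keep 30%, the upper figure becomes slightly less favourable: 88% instead of 91%.

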6.1.1 Phase II Randomized Double Blind Placebo Controlled Study

Phase II study will consist of a randomized double blind placebo controlled study involving patients who have treatment interruption due to grade 2 or 3 irAEs. Patients may receive steroids at the discretion of the treating physician prior to and during treatment with CD24Fc. As the steroids is the most commonly used SOC therapy for irAEs and it affects the severity and duration of irAE, we will separate the subjects into two groups based on the status of steroids use at registration. Each group of patients will be randomized (1:1) to receive CD24Fc vs placebo in addition to SOC treatment for irAE. Patients who are randomized to treatment with CD24Fc will receive treatment every 2 weeks for total of three treatments. Placebo group will receive 100 mL of normal saline every 2 weeks for total of three treatments. Refer to [Table 2](#) and [Figure 2](#) for treatment schedule. All patients shall complete 3 treatments.

Two weeks after completing the third treatment dose, patients will be re-evaluated for retreatment with ICI at the discretion of the treating physician and post treatment re-evaluation. Thereafter, patients will continue to end of treatment safety follow up on day 60. After the end of treatment, we will follow patients with irAE and survival by chart check every 3 months for up to 1 year.

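### At 36 per arm the one-sided Fisher test uses at most 3.8% of its 5% error rate; for a single unstratified look, Boschloo's exact test would lift power from about 81% to about 86%

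*Combined protocol and SAP*

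**What the plan says.** Section 10.3 takes Day 42 recovery to be about 50% on control and hypothesizes 80% on CD24Fc. It then states: "A sample size of 72 patients (36 in each arm) will have 81% power". The test behind that figure follows: "This result is based on one-sided" Fisher's "Exact test and significance level of 0.05". Section 6.1.1 sets equal allocation within each steroid group: "Each group of patients will be randomized (1:1) to receive CD24Fc vs placebo".

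Section 10.2 plans the same kind of test for the recovery rate, without giving a sidedness: "Comparisons between groups will be performed by Fisher's Exact tests". It also says that analyses will adjust for steroid use, but does not say how that enters the recovery comparison.

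The synopsis repeats the power calculation. It adds a group-sequential design with looks every 24 patients and average sample sizes of 46 under the null and 58 under the alternative. It gives no efficacy boundaries, and Section 10.3 does not mention the looks. Nowhere do the documents discuss the actual size of Fisher's test or name an unconditional alternative.

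**The concern.** Fisher's test conditions on the total number of recoveries. The resulting p-value is coarse, so in small samples the test rejects less often under the null than its nominal level permits. An exact unconditional test can recover part of that lost error rate and still hold type I error at or below 5%.

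The matter is worth a look here because Day 42 recovery is a co-primary endpoint and the planned power is only 81%. The trial is a small single-centre study that expects 4 to 5 patients a month. A few points of power obtained from the choice of test would otherwise have to be bought with patients.

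**Working it through.** **Inputs.** From Section 10.3: control rate 0.50, CD24Fc rate 0.80, 36 per arm, one-sided 0.05, Fisher's exact test, 81% power. From Section 6.1.1: 1:1 allocation. Assumed, because the 81% reproduces only this way: one fixed analysis of 72 patients, with no stratification.

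**Method.** Let c and t be recoveries on control and CD24Fc, each from 0 to 36, giving 37 × 37 possible tables.

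- One-sided Fisher p-value: p(c,t) = Pr(T ≥ t), where T is hypergeometric with population 72, c + t recoveries, and 36 drawn.
- Chance of rejection for a region R: the sum over tables in R of Bin(c; 36, p_c) × Bin(t; 36, p_t).
- Power sets p_c = 0.5 and p_t = 0.8. Size sets p_c = p_t = p and is maximised over p.

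**Step 1: the plan's own figure.** With R = {p(c,t) ≤ 0.05}, power is 0.8087. The stated 81% is reproduced. Other readings do not give it: the normal approximation gives 86.0% one-sided and 77.2% two-sided, and Fisher at one-sided 0.025 gives 69.6%.

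**Step 2: true size of Fisher's test.** The maximum is 3.82%, at a common rate of 50%. It is 3.21% at 65% and 2.70% at 80%.

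**Step 3: Boschloo's test.** It uses the Fisher p-value as its statistic and takes the largest cut-off whose maximum size stays within 5%. At 36 per arm the rule is to reject when the Fisher p-value is ≤ 0.0718. Maximum size is 4.82% and power is 0.8577. The gain is 85.77 − 80.87 = 4.9 points. Its rejection region contains Fisher's and adds 18 tables, so at this sample size it cannot have lower power at any pair of rates.

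**Step 4: the gain in patients.** Fisher reaches 84.8% at 41 per arm and 85.8% at 42, so it needs 2 × (42 − 36) = 12 more patients to match. At 4 to 5 a month that is 12/5 = 2.4 to 12/4 = 3 months of accrual.

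**Step 5: how stable the gain is.**

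| Patients (control/CD24Fc) | Rates | Fisher | Boschloo | Gain (points) |
|---|---|---|---|---|
| 36/36 | 50% v 75% | 65.1% | 70.6% | 5.5 |
| 36/36 | 60% v 85% | 70.0% | 76.6% | 6.6 |
| 36/36 | 55% v 80% | 66.4% | 73.8% | 7.4 |
| 36/36 | 40% v 70% | 79.5% | 80.5% | 1.0 |
| 34/36 | 50% v 80% | 81.0% | 83.8% | 2.9 |
| 35/37 | 50% v 80% | 81.5% | 85.0% | 3.4 |
| 37/35 | 50% v 80% | 79.5% | 85.6% | 6.1 |
| 34/34 | 50% v 80% | 77.3% | 83.8% | 6.5 |
| 33/36 | 50% v 80% | 77.5% | 84.5% | 7.0 |

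Gains are taken from unrounded values. Boschloo's cut-off is recomputed for each split.

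**Step 6: other tests.** The exact unconditional test on the pooled Z statistic has 84.8% power and maximum size 4.6%, so the 86% belongs to Boschloo's test by name. The uncorrected chi-square test is not a safe substitute, because its size reaches 6.2% at a 50% rate.

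**Step 7: interim looks.** If the single-look Boschloo cut-off were used at 24, 48 and 72 patients, type I error would be about 8%. Fisher at 0.05 used at all three looks would also exceed 5%, at about 7%. With no boundaries in the documents, the power of either test under the looks cannot be computed.

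**The case against.** The strongest reply is that nothing here is wrong. Section 10.3 names a valid test, its sidedness, level, rates and sample size. The 81% reproduces, and Sections 10.2 and 10.3 name the same test. On that view, Boschloo over Fisher is a preference between two exact tests. The first part stands: a reader might infer that Fisher's test is invalid or the 81% overstated, and the documents support neither. Calling it only a preference goes too far, because Boschloo's region contains Fisher's and stays within the 5% that the plan itself chose.

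Four further objections limit the claim:

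- **Interim looks.** The synopsis describes a design in which many trials would stop before 72 patients. The figures apply to a single final look. So does the stated 81%, so the comparison is like with like, but neither figure describes the sequential design.
- **Steroid adjustment.** The plan commits to adjusting for steroid use. Neither Fisher nor Boschloo does so, and if the primary test is stratified the comparison between them no longer matters.
- **Exact split.** Randomization is blocked within steroid strata, patients may move between strata, and codes are not re-used (Section 10.1). A 36/36 split is not assured, hence the range in place of a flat 5 points.
- **The gain is not free.** A reader might infer that the power costs nothing. It comes from using more of the allowed error (3.8% to 4.8% at the maximum) in a trial already tested one-sided at 0.05 with two co-primary endpoints. In 18 possible 36/36 tables, Boschloo would be significant and Fisher not.

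**Conclusion.** The point holds as an inexpensive gain in efficiency, of minor importance. For one unstratified one-sided analysis at 0.05 with 36 per arm and rates of 50% and 80%, power would be 85.8% in place of 80.9%, with maximum size 4.8% in place of 3.8%. The gain at these rates is about 3 to 7 points for 33 to 37 patients per arm. With 36 per arm it falls to 1 point at 40% versus 70%.

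A reader might take 86% as the power of the trial. The documents do not support that. The figure leaves out the interim looks and the steroid adjustment, and it says nothing about the time-to-recovery co-primary endpoint. It also depends on the one-sided 0.05 level in Section 10.3 carrying over to the analysis, which Section 10.2 does not state. At one-sided 0.025 the comparison would be 69.6% against 77.2%.

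**What to change.** In Sections 10.2 and 10.3 and in the synopsis:

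- Prespecify Boschloo's exact unconditional test, one-sided at 0.05, as the unadjusted primary test of Day 42 recovery in place of Fisher's test. Base the cut-off on the actual arm sizes.
- State that Fisher's test is supportive only and does not decide the conclusion, so that a disagreement between the two has a settled reading.
- Restate the power as about 86% for one fixed look at 36 per arm.
- If the synopsis's looks are kept as efficacy looks, give the boundaries and recalibrate the exact cut-off to them.
- If the primary test is to carry the steroid adjustment, name a stratified test instead (a Mantel-Haenszel test, for example) and compute its power separately.

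For a single look the cost is SAP wording before unblinding and standard software; recalibration to interim boundaries would add some computation. The downsides are a less familiar test, fuller use of the allowed type I error, and some results that are significant by Boschloo but not by Fisher.
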